	
4. Ability to understand and follow the study procedures and sign the informed consent
 
Exclusion Criteria
 
1. Known allergies to iodides2. Known history of cholangitis, pancreatitis, CBDS's, coagulopathy3. Known liver disease4. Women who are pregnant or breastfeeding, or for whom possibility of pregnancy was not ruled out 
1,000 patients enrolled across all centers
 
Male or female subjects undergoing laparoscopic cholecystectomy that fulfil all of the inclusion and none of the exclusion criteria.
 
Approximately 1 year
 
Primary Endpoints:
 
Detection Rate (DR) of each particular extra-hepatobiliary structure during Laparoscopic Cholecystectomy (LC) defined as the total number of patients in which the particular structure is detected before and after dissection in that arm of the Study (WLI or NIFC), divided by the total number of patients in that arm. Extra-hepatobiliary structures to be included in this assessment: Cystic Duct, Right Hepatic Duct, Common Hepatic Duct, Common Bile Duct, Cystic-CBD junction, Cystic-Gallbladder junction, and any Accessory Ducts.
 
Secondary Endpoints:
 
1. The DR for students/residents only (apart from experienced surgeons), both before and after dissection.2. Time to Clip3. Incidence of Conversion to Open Surgery4. Volume of Bleeding5. Incidence of Bile Leakage from the liver bed6. Incidence of Bile Duct Injury (BDI)7. Surgeon Confidence Level 
Test Device/Procedure:
 
Image1 SPIES (Storz Professional Image Enhancement System) Endoscopic ICG Imaging System
 
Comparator Device/Procedure:
 
Standard Image1 SPIES Endoscopic System using white light imaging (WLI) only
 
Statistical Analysis:
 
The DR (before and after dissection) between arms will be compared using the chi-square test while the number of

--	--

structures detected will be analyzed using non-parametric tests. Regression models (logistic or generalized mixed models) will be fitted to evaluate if the effect of NIFC on the primary outcomes is modified by the patient's or surgeon's characteristics or the site.

2. Introduction

a. Background

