3. Compare the mean number of procedures that required Conversion to Open using NIFC vs WLI alone.
4. Compare the mean Volume of Bleeding using NIFC vs WLI alone.
5. Compare the Incidence rate of Bile Leakage from the liver bed using NIFC vs WLI alone.
6. Compare the Incidence rate of Bile Duct Injury (BDI) using NIFC vs WLI alone.
7. Compare the mean Surgeon Confidence Level using NIFC vs WLI alone.

5. Study Endpoints

a. Primary Endpoint:

Detection Rate (DR) of each particular extra-hepatobiliary structure during Laparoscopic Cholecystectomy (LC) defined as the total number of patients in which the particular structure is detected before and after dissection in that arm of the Study (WLI or NIFC), divided by the total number of patients in that arm. Extra-hepatobiliary structures to be included in this assessment: Cystic Duct, Right Hepatic Duct, Common Hepatic Duct, Common Bile Duct, Cystic-CBD junction, Cystic-Gallbladder junction, and any Accessory Ducts.

b. Secondary Endpoints:

1. The DR for students/residents only (apart from experienced surgeons), both before and after dissection.
2. Time to Clip
3. Incidence of Conversion to Open Surgery
4. Volume of Bleeding
5. Incidence of Bile Leakage from the liver bed
6. The mean Incidence of Bile Duct Injury (BDI)
7. Surgeon Confidence Level

6. Covariates

Besides the comparison of the outcomes in both study arms, we will conduct an exploratory analysis to identify potential effect modifiers. The following baseline variables will be considered:

- 1) Patient data:
 - a) Age
 - b) Gender
 - c) BMI
- 2) Patient history/condition:
 - a) obesity
 - b) liver disease
 - c) lithiasis
 - d) surgery status (elective/urgent/emergent)
- 3) Intra-operative factors:
 - a) amount of fat covering cystic artery
 - b) amount of inflammation
 - c) presences of adhesions / scar tissue
- 4) Surgeon expertise (resident/attendant)

7. Additional Observations (NIFC group only)

a. “Reflux Maneuver”

According to previous publications, in some cases the Cystic Duct may not be seen with NIFC because the Cystic Duct may not contain ICG at the time of viewing. In those cases, a “reflux maneuver” [defined as using an atraumatic laparoscopic instrument to push on the Common Bile Duct in order to move more of the ICG from the Common Bile Duct through the Cystic Duct into the Gallbladder – thereby increasing visualization of the Cystic-Gallbladder junction] can be performed.

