Upon entry in the clinical trial, the master study database (REDCap, described later in Section 16) will randomly allocated patients to one of the study arms (1:1) within site (1:1) using a computer generated random sequence. This will provide an allocation sequence for each site. Once a patient is enrolled and a database file in REDCap is initiated for that patient, he/she will be assigned electronically to one of the study arms.

Patient will be blind to the intervention but surgeon blinding will not be feasible due to the nature of the intervention. The study will involve a considerable number of surgeons in each site, which should compensate any potential bias of some of them in favor or against either approach.

e. Flow chart

Multi-center Study Protocol: Efficacy of Near Infrared Incisionless Fluorescent Cholangiography (NIFC) during Laparoscopic Cholecystectomy

[figure not shown]
Figure 1 shows the flow chart for the study, a multi-centered randomized controlled trial (RCT) 1:1 with two arms:

1. Control: WLI

A laparoscopic cholecystectomy will be performed using Xenon white light imaging (WLI) only.

2. Experimental: NIFC

A laparoscopic cholecystectomy will be performed using both white light imaging and near infrared light imaging with indocyanine green (ICG) intravenous dye.

9. Data collection and procedures

Data will be collected before, during and at the end of surgery; and one week after surgery.

a. Pre-Op data collection

i. Patient data

- Age
- Gender
- Weight
- Height
- BMI

ii. Patient clinical characteristics

- Liver disease
- Lithiasis
- Surgical status: elective/urgent/emergent

b. Intra-Op data collection

i. For NIFC arm only

- Time of ICC administration
- Was there any Adverse Reaction? If so, what happened and how was the patient treated?

ii. For both arms: PRIOR to dissection

- Categorize initial visualization
 - Amount of fat
 - Amount of inflammation
 - Presence of adhesions / scar tissue
- Remove the fat from the Calot's triangle area, retract the gallbladder and Hartmann's pouch
- Surgeon/Observer documents which extra-hepatic biliary structures are identified without doubt
- Start Dissection. Document the time hilar dissection was begun (baseline time)

iii. For both arms: AFTER dissection

- Surgeon/Observer documents which extra-hepatic biliary structures are identified without doubt
- Time to Clip: Document the time the Cystic Duct was clipped
- Volume of Bleeding
- Incidence of Bile Leakage

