3. After removing the fat from the gallbladder area, lifting the gallbladder over the liver, and grabbing the Hartman's pouch to visualize the Calot's triangle, but PRIOR TO DISSECTION, the Researcher will use NIFC to determine what extra-hepatic biliary structures can be specifically identified. This involves toggling the light source back and forth between STD mode (WLI) and ICG mode (NIFC). Of note: because one of the goals of the Study is to evaluate NIFC as a teaching tool, residents and juniors should record what structures they were able to identify by themselves before any intervention of the attendant surgeon.
4. Then, AFTER DISSECTION, a similar assessment of what extra-hepatic biliary structures can be specifically identified using NIFC will be performed.
5. Anatomic anomalies of the biliary system will be documented on the case form and if an anatomic variation is found, a snap shot photo will be taken in addition to the video.
6. Immediately before clipping or proceeding with open surgery, the total time from Step 1 will be recorded, known herein as the "Time to Clip";
7. Before leaving the operation room, all participant surgeons and observers will complete the Intra-Operative Case Report Form (Appendices D and E, respectively).

d. Post-Operative Case Report Form

During the standard follow-up exam, typically 7-10 day post-op, the Researcher will complete the Post-Operative Case Report Form (Appendix F).

e. Bile Duct Injury Form (if needed)

If the procedure results in a bile duct injury, the operating surgeon will complete the ancillary Bile Duct Injury Form (Appendix G).

13. Statistical Plan

a. Sample size

We estimate that the six participant centers will be able to enroll a minimum of 1000 patients in a 12 months period. Table XX shows the minimum effect size (increase in the rate of detection) that we will be able to detect with a 90% power or more, 5% level of significance, one-side test, when the detection rate in the control group are the ones indicated in the first column.

Structure	Before dissection		After dissection	
	DR control group	DR increase (effect size)	DR control group	DR increase (effect size)
Cystic	50%	10%	100%	--
Right Hepatic Duct	40%	10%	80%	7%
Common Hepatic Duct	46%	10%	70%	8%
Common Bile Duct	46%	10%	96%	3%
Cystic-CBD junction	29%	9%	60%	9%
Cystic-Gallbladder junction	60%	9%	70%	8%
Accessory Ducts	1%	3%	2%	4%

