Regarding the main secondary outcome, incidence of injuries, the power to detect a drop from 8/1000 in the control arm to 2/1000 in the intervention arm, with a sample size of 500 patients per arm is 15%. Regretfully, with an achievable sample size as the one proposed above, the study will not have enough power to detect a drop in the incidence as important as the one considered.

b. Data Analysis

In general, descriptive statistics including frequencies and means will be used to characterize patient's baseline characteristics in both study arms. Analyses are designed to test the following hypotheses based on the primary objectives: Compared to those in the control arm, surgeons using NIFC will be able to identify a) more frequently the gallbladder cystic union (both before dissection and before clipping); b) a larger number of hepato-biliary structures and; c) more frequently some of the five hepato-biliary structures. We will test the first hypothesis using the chi-square test, the second one using non-parametric test (e.g. Kruskal-Wallis) and the third one using generalized mixed or hierarchical models to account for the clustering induced by the patient.

Multi-center Study Protocol: Efficacy of Near Infrared Incisionless Fluorescent Cholangiography (NIFC) during Laparoscopic Cholecystectomy

Regression models (logistic or generalized mixed models) will be fitted including covariates to evaluate if the effect of NIFC on the primary outcomes is modified by the patient's or surgeon's characteristics and site.

Regarding secondary outcomes we will use the Fisher's exact test or Chi square test (as needed) to compare proportion of patients with bile duct injury, open surgery or bleeding. Time to clipping and time to end of surgery will be compared between arms using the Kruskal-Wallis' test. Regression models will be used when possible -we expect very low incidence of injuries and open surgeries- to evaluate patient's and surgeon's effect modification.

Finally, for those outcomes specific for the NIFC group we will use logistic or generalized linear models to assess whether the reported helpfulness of the NIR light or the reflux maneuver is associated to patient's characteristics or surgeon's experience.

All statistical analysis will be conducted in R software.

14. Anticipated Problems and Solutions

a. Lower than expected Enrollment

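### The primary arm comparisons use neither site nor the pre-operative covariates, leaving a modest and nearly free gain in precision unused

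*Combined protocol and SAP*

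**What the plan says.** Section 13.b sets three primary hypotheses:

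- (a) Detection of the cystic-gallbladder junction: "We will test the first hypothesis using the chi-square test".
- (b) The number of structures identified: a non-parametric test, with Kruskal-Wallis as the example.
- (c) The individual structures: a generalized mixed or hierarchical model, whose only stated purpose is to handle correlation within patient.

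The Statistical Analysis entry in section 1 says that detection rates before and after dissection "between arms will be compared using the chi-square test". None of these comparisons names a baseline covariate or site.

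Covariates appear elsewhere. Section 6 says "we will conduct an exploratory analysis to identify potential effect modifiers", and the regression models in 13.b include covariates and site to see whether they modify the NIFC effect.

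Section 8.d allocates patients "to one of the study arms (1:1) within site (1:1) using a computer generated random sequence". Sections 9.a and 12.b and the Pre-Op Case Report Form (Appendix C) collect age, sex, BMI and surgery status at admission. Section 14.b expects no missing covariates.

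The table in 13.a gives detectable increases "with a 90% power or more, 5% level of significance, one-side test", for centres that "will be able to enroll a minimum of 1000 patients in a 12 months period". Section 13.a later uses 500 patients per arm.

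**The concern.** Detection probably depends on the patient as well as on the light source. Section 2.b names obese patients and those with inflammatory processes as cases where Calot's triangle is hard to assess. BMI measures the first directly. Surgery status is a plausible stand-in for the second, although that link is an inference. Detection may also differ between sites.

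In a randomised trial, adjusting for variables that predict the outcome removes explained variation from the error of the arm comparison. It narrows the interval without more patients or data. Leaving out the factor within which patients were randomised also makes the chi-square test somewhat conservative if detection differs by site.

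Two things are at stake: some precision, and the discipline of having one adjusted main-effect analysis fixed in advance. Testing interactions is not the same as adjusting the arm comparison, so the planned regressions do not fill this gap.

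**Working it through.** **Inputs from the documents.** 500 per arm, one-sided 5%, power of at least 90% (13.a). Cystic-gallbladder junction: 60% plus 9 points before dissection, 70% plus 8 points after. The common hepatic duct after dissection is also 70% plus 8.

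**Input assumed.** R², the share of outcome variance explained by the covariates. The documents give nothing from which to derive it. To set a range I assumed log-odds effects of -0.2 to -0.6 per SD of BMI, -0.4 to -1.0 for urgent or emergent surgery in 25% of patients, -0.1 to -0.2 per SD of age, and -0.1 to -0.3 for sex. Simulated R² was then about 2% (weak), 6% (middle) and 12% (strong).

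**Step 1: reproduce the plan's figure.** For 70% against 78%:

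- Null standard error: √(2 × 0.74 × 0.26 / 500) = 0.02774
- Alternative standard error: √((0.70 × 0.30 + 0.78 × 0.22) / 500) = 0.02763
- Power: Φ((0.08 − 1.645 × 0.02774) / 0.02763) = Φ(1.244) = 89.3%

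For 60% against 69% the same formula gives 90.9%. The 13 cells with an effect size run from 89.3% to 94.4%, so the table is unadjusted and one-sided. At a 70% control rate the increase with exactly 90% power is 8.10 points. The table prints whole points, so the 89.3% is rounding.

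**Step 2: apply adjustment.** Replace n by n / (1 − R²), so standard errors shrink by √(1 − R²). The 95% CI half-width for 70% against 78% is 1.96 × 0.02763 × √(1 − R²). Equivalent extra patients are 1000 × (1 / (1 − R²) − 1).

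| R² (assumed) | Power, 70% v 78% | 95% CI half-width (points) | Equivalent extra patients |
|---|---|---|---|
| 0% | 89.3% | 5.41 | 0 |
| 2% | 89.9% | 5.36 | 20 |
| 6% | 90.9% | 5.25 | 64 |
| 12% | 92.4% | 5.08 | 136 |

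For 60% against 69%, one-sided power goes from 90.9% to 91.4% at 2% and 93.3% at 10%. Under a two-sided 5% test the two comparisons start lower, at 82.3% (70% v 78%) and 84.6% (60% v 69%), and reach 86.1% and 88.1% at an R² of 10%.

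**Step 3: check by simulation.** I ran 1,500 trials of 1,000 patients per setting, 60% against 69%, with one prognostic score standing in for the covariates and no site effect. The variance of the standardised difference relative to the unadjusted one was 1.00, 0.99, 0.91 and 0.86 at R² of 0, 0.02, 0.07 and 0.14. With no association, power was 89.7% either way: no gain and no loss.

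**Step 4: where the model will not fit.** Expected counts of the rarer outcome, from the table's rates:

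- Accessory ducts before dissection: 500 × 0.01 + 500 × 0.04 = 25
- Accessory ducts after dissection: 500 × 0.02 + 500 × 0.06 = 40
- Common bile duct after dissection: 500 × 0.04 + 500 × 0.01 = 25 non-detections
- Cystic duct after dissection: the control rate is already 100%

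The proposed model has 11 to 14 coefficients besides the intercept: arm 1, site 5 to 8 (13.a speaks of six centres, 8.b lists nine), BMI, age and sex 1 each, and surgery status 2. Twenty-five events give about two per coefficient. The next smallest cell, the right hepatic duct after dissection, has 500 × 0.20 + 500 × 0.13 = 165 non-detections, which is 12 to 15 per coefficient.

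**The case against.** The strongest reply is that nothing here is an error. A chi-square test in a 1:1 randomised trial is valid, and no bias or false-positive risk has been shown. That stands. A reader might infer that the primary analysis is invalid, or that a trial at 89.3% power needs adjustment to rescue it. The documents support neither: randomisation protects the unadjusted comparison, and the shortfall is whole-point rounding.

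The gain is also small and rests on assumed associations. In the weak case power stays just below 90%. Nor is power scarce everywhere. Before dissection, one series cited in 2.b reports NIFC rates of 93%, 88% and 91% for the cystic, common hepatic and common bile ducts, against table control rates of 50%, 46% and 46%. Differences that large need no help. Those data are observational, however, and no rate is cited for the cystic-gallbladder junction.

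Section 2.b raises obesity and inflammation as groups in whom NIFC might help more, which is a rationale for effect modification. It also says that assessment is difficult in these patients, so an association with detection is a reasonable expectation, but the plan does not quantify it.

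A reader might also take the four variables as shown to be recorded before allocation. The documents do not settle this. Allocation follows the opening of the REDCap file (8.d), and the form is completed at admission (12.b). Allocation could hardly change age, sex or BMI. Surgery status is the one to watch, although 8.c has the surgeon set the indication and date before the study is introduced.

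**Conclusion.** The point holds as a free improvement of modest size. Hypotheses a and b are tested without covariates or site, the model for hypothesis c names neither, and the covariate models already planned address effect modification only. At an assumed 2% to 12% of variance explained, the standard error falls by 1% to 6%, since √0.98 = 0.990 and √0.88 = 0.938. That is worth about 0.6 to 3.1 points of power in the 70%-to-78% cells. It will rarely change a conclusion. I have put no figure on the effect of site, because the documents give no variation between sites. The reading of the text is firm; the size of the gain is conditional on the assumed associations.

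**What to change.** In 13.b, before data lock:

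- Make the primary estimate for each structure and time point a standardised (marginal) detection-rate difference with 95% CI, from a logistic model with arm, site, BMI (continuous), age, sex and surgery status as recorded pre-operatively. This stays on the plan's detection-rate scale and avoids a conditional odds ratio.
- Exclude the gradings of fat, inflammation and adhesions. Section 6 calls them baseline variables, but an unblinded surgeon records them during the operation.
- Add the same covariates and site to the mixed model for hypothesis c. Use a proportional-odds model with them for the number of structures.
- Keep the chi-square test as a sensitivity analysis.
- Name in advance the cells that get an unadjusted or site-stratified test: accessory ducts at both time points, and cystic duct and common bile duct after dissection. Alternatively, set a minimum event count pooled over arms. Either way the switch cannot depend on the results by arm.

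The cost is some SAP wording and a few lines of R. The covariate list must be locked in advance, and no new data are needed.

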The studies described above are observational and so far no randomized clinical trial has been published evaluating the efficacy of NIFC to improve the identification of the extra-hepatic biliary structures. Additionally it would be relevant to investigate the ability of the NIFC to reduce intraoperative bleeding, duration of laparoscopic cholecystectomy. Further, it is central to assess whether NIFC can improve the outcomes in some subpopulation of patients for whom the evaluation and dissection of the Calot's triangle is difficult, e.g. obese patients or patients undergoing inflammatory processes. Finally, the potential use of NIFC as a training tool in laparoscopic surgery is still to be studied.

c. Strengths and Limitations

The strength of the study is the ability to investigate whether the extra-hepatic biliary tract is more visible using NIFC when compared with white light (WLI) alone. It is a multicenter study with diverse patient populations and surgeons from different countries/continents that will validate this method globally.

Limitations may include impossibility to randomize by surgeon.

3. Study Overview

The Study is designed to compare the effectiveness of Near Infrared Fluorescence Cholangiography (NIFC) to standard white light imaging (WLI) in visualizing and identifying the main biliary and hepatic structures (Cystic Duct, Right Hepatic Duct, Common Hepatic Duct, Common Bile Duct, Cystic-CBD junction, Cystic-Gallbladder junction and any Accessory Ducts) during laparoscopic cholecystectomy.

4. Study Objectives

a. Primary Objective:

Multi-center Study Protocol: Efficacy of Near Infrared Incisionless Fluorescent Cholangiography (NIFC) during Laparoscopic Cholecystectomy

Demonstrate that NIFC performs better than standard white light (WLI) alone in visualizing and identifying extra-hepatobiliary structures (Cystic Duct, Right Hepatic Duct, Common Hepatic Duct, Common Bile Duct, Cystic-CBD junction, Cystic-Gallbladder junction, and any Accessory Ducts) before and after dissection during Laparoscopic Cholecystectomy (LC).

b. Secondary Objectives:

1. Demonstrate that NIFC is an effective teaching tool to assist students and residents present in the O.R. during the procedure to identify extra-hepatobiliary structures (before/after dissection).
2. Demonstrate that the Time to Clip, which is defined as the time from the moment Calot's Triangle is first visualized to when the clip is applied, is reduced when using NIFC vs WLI alone.

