3. AFTER-DISSECTION

A. Document visualization of extra-hepatic biliary anatomy:

For both arms, scope the Calot's triangle area using STD (white-light) mode. If in the NIFC arm, toggle between STD and ICG modes on light source as needed. Check the appropriate boxes below based on what is visible:

	Yes	Maybe	No
Cystic Duct			
Right Hepatic Duct			
Common Hepatic Duct			
Common Bile Duct (CBD)			
Cystic-CBD junction			
Cystic-Gallbladder junction			
Accessory Ducts			

B. For NIFC Arm Only: "Reflux Maneuver" Attempted? Yes No

Repeat the Reflux Maneuver. Check the appropriate boxes based on what is visible:

	Yes	Maybe	No
Cystic Duct			
Cystic-CBD junction			
Cystic-Gallbladder junction			

4. Time to Clip: Time the Cystic Duct was clipped: _____ AM / PM

5. Volume of Bleeding: _____ mL in the bucket/bag or from anesthesia chart at the conclusion of the procedure

6. Bile Leakage: No Yes If yes, Liver bed Other: _____ Did NIFC help identify leak? Yes No

7. Anatomic Anomalies: No Yes If yes, describe: _____

If yes, do you feel NIFC helped you identify this anomaly? Yes No N/A (WLI arm)

8. Was IOC performed? Yes No

9. Were CBD Stones present? Yes No Not Checked

10. Was the procedure converted to Open? Yes No

If yes, explain why: _____

11. Was there a Bile Duct Injury (BDI) during the surgery? Yes No

If yes, complete the BDI Form as described in the Study Protocol.

12. SURGEON FEEDBACK after NIFC:

Did you feel NIFC made your procedure SAFER? Yes No

Were you more CONFIDENT using NIFC vs WLI alone? Yes No

Would you PREFER to use NIFC again vs WLI alone? Yes No

e. Intra-Op Case Report Form – Observer

Near Infrared Incisionless Fluorescent Cholangiography (NIFC)

INTRA-OPERATIVE CASE REPORT FORM - OBSERVER

INSTITUTION: _____

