<hr/> 
1. Length of hospital stay: _____ (days)
 
2. Was patient readmitted: No  Yes  If Yes, complete the following:
 
Days after discharge: _____ (NOTE: Day of Surgery is Day "0")Reason for readmission: _____Treatment administered: _____Length of stay: _____ (days) 
3. Death (30 d): No  Yes  If Yes, cause of death: _____
 
4. Complications: No  If No, you have completed this form. Yes  If Yes, please continue...
 
Indocyanine green drug reactions: No  If No, skip to surgical complications. Yes  If Yes, continue
Flushing? No  Yes  If yes, please complete:
Treatment required? No  Yes If Yes, what treatment: _____Urticaria? No  Yes  If yes, please complete:
Treatment required? No  Yes If Yes, what treatment: _____Other possible drug reaction? No  Yes  If Yes, please complete:
Describe: _____Onset (day of surgery is "0"): _____Duration (Hours): _____Treatment required? No  Yes If Yes, what treatment: _____ <hr/> 
MULTICENTER TRIAL
 
Page 1 of 2
 
POSTOP-CRF v1.0
		

Near Infrared Incisionless Fluorescent Cholangiography (NIFC)

2

POST-OPERATIVE FORM

b. Hemorrhage? No Yes If Yes, please complete:

- i. ... requiring transfusion? No Yes
- ii. ... requiring re-operation? No Yes
- iii. ... requiring longer hospitalization? No Yes

c. Intra-abdominal pain in right upper quadrant? No Yes

d. Bile leak (without bile duct injury)? No Yes If Yes, please complete:

- i. ... requiring percutaneous drainage? No Yes
- ii. ... requiring reoperation? No Yes
- iii. ... treated with percutaneous drainage only? No Yes
- iv. ... treated with transpapillary stent? No Yes
- v. ... treated with percutaneous drainage and transpapillary stent? No Yes

vi. Source of leak:

1. cystic duct stump leak? No Yes
2. liver bed? No Yes
3. never determined? No Yes

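### Secondary objective 4 compares mean volume of bleeding, but Section 13.b plans only a test of the proportion of patients with an undefined *bleeding* outcome

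*Combined protocol and SAP*

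**What the plan says.** Section 4.b, item 4, sets the objective: "Compare the mean Volume of Bleeding using NIFC vs WLI alone". The matching endpoint in Section 5.b is "4. Volume of Bleeding", with no threshold and no yes/no form. Section 9.b.iii collects it in both arms. Item 5 of the surgeon's intra-operative form (Appendix d) asks for "mL in the bucket/bag or from anesthesia chart at the conclusion of the procedure".

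Section 13.b names bleeding once. It gives Fisher's exact or chi-square tests "to compare proportion of patients with bile duct injury, open surgery or bleeding". The next sentence deals with secondary outcomes that are not binary: "Time to clipping and time to end of surgery will be compared between arms using the Kruskal-Wallis' test". Volume is not in it.

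The only yes/no bleeding item on any form is in the post-operative form (Appendix f, item 4.b): "Hemorrhage? No Yes If Yes, please complete". Section 13.b does not refer to it.

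**The concern.** The objective, the endpoint and the form all concern a continuous volume, while the analysis plan tests a proportion. A test of proportions neither estimates nor tests a difference in mean volume. An analyst who followed 13.b literally would have nothing to report for objective 4.

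The binary outcome is also undefined. If it is meant as a split of the mL value, the split point is open and could be settled after the data are seen. Surgeons are not blinded (Section 8.d), which adds to the value of fixing the analysis beforehand.

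The protocol gives the question some weight. Section 2.b, on what earlier studies left open, says that "it would be relevant to investigate the ability of the NIFC to reduce intraoperative bleeding".

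**Working it through.** **Step 1. Set the passages side by side.**

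| Place | What it specifies | Scale |
|---|---|---|
| Section 4.b, objective 4 | mean volume, NIFC against WLI | continuous |
| Section 5.b, endpoint 4 | volume | continuous |
| Section 9.b.iii | volume, both arms | continuous |
| Appendix d, item 5 | mL at the end of the procedure | continuous |
| Section 13.b | proportion with *bleeding*, Fisher or chi-square | binary |

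**Step 2. Look for another sentence that covers volume.**
- Kruskal-Wallis is assigned by name to two times only.
- Means are planned only to describe baseline characteristics.
- Regression for secondary outcomes is for effect modification by patient and surgeon, where feasible.
- The statistical paragraph in the Section 1 summary covers detection rates, the number of structures detected, and effect modification on the primary outcomes.

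None of these compares volume between arms.

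**Step 3. Try each reading of *bleeding*.**
1. *A split of the mL value.* The intra-operative form has no yes/no bleeding field, and no cut-off appears anywhere.
2. *The post-operative hemorrhage item.* This is a complication recorded at the follow-up visit, typically at 7-10 days. Nothing is split, but volume then has no between-arm analysis.

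Neither reading answers objective 4. The documents state no figure for bleeding, so there is none to reproduce.

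**Step 4. Illustrate the cost of reading 1.** The 500 per arm comes from Section 13.a. The distribution, shift and split points are assumptions.

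Let p be the share of one arm above the cut, f the density and q the cut point. For a shift, the asymptotic efficiency of the split relative to a rank test is

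[f(q)² / (p(1−p))] / [12(∫f²)²].

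The denominator is 3/π for the normal. For the logistic the whole expression reduces to 3p(1−p). For the double-exponential, with p ≤ 0.5, it reduces to (4/3)·p/(1−p).

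| Assumed shape | p = 50% | 25% | 10% | 5% |
|---|---|---|---|---|
| Normal | 67% | 56% | 36% | 23% |
| Logistic | 75% | 56% | 27% | 14% |
| Double-exponential | 133% | 44% | 15% | 7% |

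For power, take a normal shift of 0.181 SD and a two-sided 5% test.
- Rank test: Φ(0.181·√(250·3/π) − 1.96) = Φ(0.84) = 80%.
- Chi-square at a 50% split, with lower volume in the NIFC arm: the proportions are 0.500 and 1 − Φ(0.181) = 0.428, and the pooled value is 0.464. The null standard error is √(2·0.464·0.536/500) = 0.0315, and the alternative standard error is also 0.0315. Power is Φ((0.0718 − 1.96·0.0315)/0.0315) = Φ(0.32), about 62%.
- The same formula gives 53%, 36% and 24% at the 25%, 10% and 5% splits.

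A simulation of 4,000 runs gave 81% for the rank test and 64%, 55%, 37% and 26% for the four splits, within about 2 points of the formula.

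**The case against.** The best counter-reading is that *bleeding* in 13.b means a complication and not a split volume. Section 15.b lists the same three risks together: bile duct injury, bleeding and conversion to open surgery. The follow-up list in Section 9.c and the post-operative form also put hemorrhage beside bile duct injury. This makes reading 2 somewhat likelier, but it does not define the term. Under that reading volume has no planned comparison, so the main point stands.

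Three further objections carry some weight.
- Every efficiency and power figure belongs to reading 1 and rests on assumptions. The range runs from no loss (133%) to 7%, and a normal shift is a rough model for a volume that cannot be negative. The figures show that the cut-off matters; they do not measure a loss in this trial.
- Under reading 1, *bleeding* could simply mean any volume above zero, which leaves no cut-off to choose. But if nearly every patient loses some blood, this is a split near 95%, where efficiency under the normal model is again about 23%.
- The protocol uses *mean* loosely. It also speaks of a mean number of conversions and a mean incidence of bile duct injury, both binary outcomes. A strict difference in means may not be intended, so the fix should allow the objective to be reworded.

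It is also true that 13.b names no test for bile leakage or surgeon confidence, so volume is not the only secondary endpoint without a matching analysis. It differs in that a test is assigned to bleeding and does not fit the endpoint.

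**Conclusion.** The concern holds. Objective 4 has no matching analysis: the one planned between-arm test that names bleeding is binary, undefined, and addresses a different question from the difference in volume. This conclusion rests on the text alone and does not depend on which reading of *bleeding* was intended.

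The consequence is certain under both readings: the plan gives no estimate of the difference in volume. Any loss of power arises only under reading 1 and cannot be sized from the documents.

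The weight is moderate. Section 13.a treats injury, not bleeding, as the main secondary outcome, and neither the primary analysis nor the sample size is touched. The point should be corrected before analysis, but it does not threaten the trial's main conclusion.

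**What to change.** Change Section 13.b in three respects.

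1. **Add volume to the rank-test sentence.** List volume of bleeding (mL) with the two times already compared by Kruskal-Wallis. With two arms this is the Wilcoxon rank-sum test.
2. **Report an estimate that matches the objective.** Give the between-arm difference in mean mL with a 95% confidence interval, for example by bootstrap to allow for skew and zeros, with the median difference alongside. A rank test does not test means, so state that the mean difference and its interval answer objective 4. If means are not intended, reword objective 4 instead.
3. **Resolve the binary term.** Delete *bleeding* from the Fisher/chi-square list, or define it there as the post-operative yes/no hemorrhage item.

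Stratifying the comparison by site, within which patients are randomized, is a reasonable option but not essential.

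The cost is one or two sentences, written before the data are analysed. Both the mL volume and the hemorrhage item are already collected, so no form, visit or sample size changes.
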